3.0 LIST OF ABBREVIATIONS

AE	adverse event
ALP	alkaline phosphatase
ALT	alanine aminotransferase
AST	aspartate aminotransferase
AUC	area under the curve
BUN	blood urea nitrogen
Cmax	maximum observed serum concentration
COMT	catechol- O -methyltransferase
CRO	contract research organization
CYP	Cytochrome P-450
FDA	Food and Drug Administration
GCP	Good Clinical Practice
γ-GTP	γ-glutamyl transpeptidase
hCG	human chorionic gonadotropin
ICH	International Conference on Harmonisation
INN	international nonproprietary name
INR	international normalized ratio
LDH	lactate dehydrogenase
MAO	Monoamine oxidase
MDS	Movement Disorders Society
MedDRA	Medical Dictionary for Regulatory Activities
MHRA	Medicines and Healthcare products Regulatory Agency
PDQ-39	The 39-item Parkinson's disease questionnaire
PMDA	Pharmaceuticals and Medical Devices Agency
PT	preferred term
PTE	pretreatment event
QOL	quality of life
SOC	system organ class
SUSARs	suspected unexpected serious adverse reactions
TEAE	treatment-emergent adverse event
UPDRS	unified Parkinson's disease rating scale
WHO	World Health Organization

4.0 INTRODUCTION

4.1 Background

Parkinson's disease is the second most common neurodegenerative disorder of the central nervous system after Alzheimer's disease. The prevalence of Parkinson's disease is estimated to be 100-150/100,000 in the Japanese population, mostly affecting elderly people with peak age in the late 50s to 60s [1]. A significant increase in the number of patients is expected as the population ages in the future.

The 4 major symptoms of Parkinson's disease are resting tremor, muscle rigidity (muscle stiffness), bradykinesia, and postural instability. These motor symptoms are suspected to occur due to damage or death of substantia nigra dopaminergic neurons in the midbrain, followed by a reduction in dopamine volume in the striatum.

The Japanese therapeutic guideline recommends initially treating motor symptoms of Parkinson's disease with levodopa or a dopamine agonist, in principle, and rich evidence with these drugs used as first-line therapy are available [2].

In clinical practice overseas, the efficacy of initial treatment with MAO-B inhibitors has been demonstrated in Parkinson's disease and the therapeutic algorithm recommends MAO-B inhibitors as the first-line treatment for mild Parkinson's disease in addition to levodopa and dopamine agonists [3][4]. In Japan, selegiline is one of the MAO-B inhibitors available but not approved for first-line treatment of Parkinson's disease. If clinical development of MAO-B inhibitors is promoted in Japan, treatment options for patients with mild or early Parkinson's disease may expand.

TVP-1012 (INN: rasagiline) is a MAO-B inhibitor without an amphetamine structure. In comparison with selegiline, TVP-1012 is characterized by (1) a 5 to 10-fold MAO-B inhibitory effect, and (2) easy drug management due to not having an amphetamine structure and not being designated as ingredient in narcotics. As of September, 2014, rasagiline has been approved in 53 countries in Europe, the United States, and East Asian countries as a monotherapy for early Parkinson's disease, and also as concomitant therapy with levodopa for Parkinson's disease. Currently, clinical development for TVP-1012 as monotherapy for early Parkinson's disease and as an add-on therapy to levodopa for Parkinson's disease is ongoing in Japan.

CONFIDENTIAL

Efficacy Summary

A thick black horizontal bar, likely a redacted section of text.

Safety Summary

Term	Percentage
GMOs	~75%
Organic	~95%
Natural	~95%
Artificial	~75%
Organic	~95%
Natural	~95%
Artificial	~75%
Organic	~95%
Natural	~95%
Artificial	~75%
Organic	~95%
Natural	~95%
Artificial	~75%

CONFIDENTIAL

4.2 Rationale for the Proposed Study

Based on these results, this study was planned to evaluate the efficacy and safety of long-term extension administration with TVP-1012 in Japanese patients with early Parkinson's disease who have completed the preceding study (TVP-1012/CCT-001). The comprehensive evaluation of the efficacy and safety of TVP-1012 in early Parkinson's disease will be performed based on the results of this study, Study TVP-1012/CCT-001, and overseas clinical studies.

The clinical development of TVP-1012 as an add-on to levodopa for Parkinson's disease is ongoing in Japan. Currently, a Phase 2/3 study (TVP-1012/CCT-002) and a Phase 3 study (TVP-1012/OCT-002) are underway.

CONFIDENTIAL

5.0 STUDY OBJECTIVES AND ENDPOINTS

5.1 Objectives

5.1.1 Primary Objective(s)

- To evaluate the long-term safety of TVP-1012 (1 mg/day) in Japanese patients with early Parkinson's disease

5.1.2 Secondary Objectives(s)

- To evaluate the long-term efficacy of TVP-1012 (1 mg/day) in Japanese patients with early Parkinson's disease

5.2 Endpoints

5.2.1 Primary Endpoint

- Adverse events (AEs)

5.2.2 Secondary Endpoints

- Clinical laboratory test values, vital signs, electrocardiogram (ECG), and weight
- Movement Disorder Society-Unified Parkinson's Disease Rating Scale (MDS-UPDRS) Part II + Part III total score

5.2.3 Additional Endpoints

- MDS-UPDRS Part I total score
- MDS-UPDRS Part II total score
- MDS-UPDRS Part III total score
- MDS-UPDRS Part IV total score
- MDS-UPDRS tremor score
- MDS-UPDRS bradykinesia score
- MDS-UPDRS muscle rigidity score
- MDS-UPDRS individual score
- Parkinson's Disease Questionnaire-39 (PDQ-39) Summary Index scores for individual domain

6.0 STUDY DESIGN AND DESCRIPTION

6.1 Study Design

Patients will make a total of 7 visits in this study, i.e., at Weeks 26, 29, 32, 36, 40, 46 and 52 of the treatment period, to undergo designated tests, observations, and assessments.

[figure not shown]
This is a multicenter, open-label, long-term, extension, phase 3 study to evaluate the safety and efficacy of long-term administration of TVP-1012 at 1 mg for another 26 weeks in patients with early Parkinson's disease who have completed the 26-week treatment period in the preceding TVP-1012/CCT-001 study.

Among participants of the TVP-1012/CCT-001 study, those consenting to participate in this study prior to undergoing the tests, observations, and assessments at Week 26 of the treatment period (VISIT 8) in the preceding study, and fulfilling the eligibility criteria will be enrolled in this study. From the day after the VISIT 8 of the preceding study, subjects will receive TVP-1012 1 mg once daily for 26 weeks in an unblinded manner.

The visit numbers in this study will be continued from the preceding study, and the study visit week will be counted from the start of the treatment period in the preceding study.

This study will be conducted in the same study sites as those of the preceding study (55 sites) and the number of subjects to be enrolled in this study is estimated to be 182 subjects after considering dropouts in the preceding study.

Schematic of Study Design is included as Figure 6.a. A schedule of study procedures is listed in Appendix A.

V: VISIT

* Informed consent for this study must be obtained prior to tests, observations, and assessments at Week 26 of the treatment period in the preceding study. Those who consent to participate in this study and fulfilling the eligibility criteria will be enrolled in this study. Subjects will start dosing from the day after the VISIT 8.

Figure 6.a Schematic of Study Design

CONFIDENTIAL

6.2 Justification for Study Design, Dose, and Endpoints

6.2.1 Justification for Study Subject

To evaluate the safety and efficacy of long-term administration of TVP-1012 in Japanese patients with early Parkinson's disease, this study will target subjects who have completed the preceding study and were assessed as not demonstrating safety concerns in the opinion of the investigator or sub-investigator.

6.2.2 Justification for Study Design

This open-label, long-term extension study has a common study design that allows for the evaluation of long-term safety. This study was designed as an extension study following the preceding study, to collect pertinent data on long-term administration in an efficient manner.

See Section 13.3 for Sample Size Justification.

6.2.3 Justification for Dose Regimen

[REDACTED]

In the preceding study, 1 mg of TVP-1012 or placebo was administered for 26 weeks to evaluate the efficacy and safety of TVP-1012 1 mg.

In this study, the dose of 1 mg of TVP-1012 will be maintained for subjects treated with 1 mg of TVP-1012 in the preceding study, to evaluate administration at 1 mg for 52 weeks. In addition, subjects treated with placebo in the preceding study will be switched to 1 mg of TVP-1012 in this study, to evaluate administration at 1 mg for 26 weeks, for the purpose of evaluating a large number of subjects as much as possible.

[REDACTED]

CONFIDENTIAL

6.2.4 Justification for Treatment Period

Parkinson's disease is a progressive disease and long-term administration is anticipated when TVP-1012 is prescribed. Therefore, another 26-week extension of treatment was planned following the 26-week treatment in the preceding study to evaluate the long-term safety of TVP-1012 for 6 months and 12 months.

6.2.5 Justification for Endpoints

In this study, the long-term safety and efficacy of TVP-1012 following the preceding study will be evaluated. As the safety and efficacy will be evaluated in pooled data from this and preceding studies, the same endpoints used for the preceding study were set.

Safety evaluation is the primary objective of this study. Of the safety evaluation variables in the preceding study, the frequency of adverse events (AEs) will be used as the primary endpoint and clinical laboratory test results, vital signs, ECGs, and weight will be used for the assessment of secondary endpoints.

In addition, MDS-UPDRS Part II + Part III total score, which was the primary efficacy endpoint in the preceding study, will be used as a secondary endpoint. The efficacy endpoints in the preceding study other than MDS-UPDRS Part II + Part III total score will be set as additional endpoints.

6.3 Premature Termination or Suspension of Study or Investigational Site

6.3.1 Criteria for Premature Termination or Suspension of the Study

The study will be completed as planned unless one or more of the following criteria are satisfied that require temporary suspension or early termination of the study.

- New information or other evaluation regarding the safety or efficacy of the study medication that indicates a change in the known risk/benefit profile for the compound, such that the risk/benefit is no longer acceptable for subjects participating in the study.

- Significant violation of Good Clinical Practice (GCP) that compromises the ability to achieve the primary study objectives or compromises subject safety.

6.3.2 Criteria for Premature Termination or Suspension of Investigational Sites

A study site may be terminated prematurely or suspended if the site (including the investigator) is found in significant violation of GCP, protocol, or contractual agreement, is unable to ensure adequate performance of the study, or as otherwise permitted by the contractual agreement.

6.3.3 Procedures for Premature Termination or Suspension of the Study or the Participation of Investigational Site(s)

In the event that the sponsor, an institutional review board (IRB) or regulatory authority elects to terminate or suspend the study or the participation of an investigational site, a study-specific procedure for early termination or suspension will be provided by the sponsor; the procedure will be followed by applicable investigational sites during the course of termination or study suspension.

7.0 SELECTION AND DISCONTINUATION/WITHDRAWAL OF SUBJECTS

All entry criteria, including test results, need to be confirmed prior to the administration of the investigational drug.

7.1 Inclusion Criteria

Subject eligibility is determined according to the following criteria:

1. In the opinion of the investigator or sub-investigator, the subject is capable of understanding and complying with protocol requirements.
2. The subject signs and dates a written, informed consent form and any required privacy authorization prior to the initiation of any study procedures.
3. The subject has completed the preceding study (TVP-1012/CCT-001 study).
4. The subject has shown no safety issues during the study treatment in the preceding study, in the judgment of the investigator or sub-investigator.
5. A female subject of childbearing potential* who is sexually active with a nonsterilized* male partner agrees to use routinely adequate contraception* from signing of informed consent to 1 month after the last dose of the investigational drug.

*Definition of female subjects of chiledbearing potential is defined in Section 9.1.10.

Contraception and Pregnancy Avoidance Procedure and reporting responsibilities are defined in Section 9.1.11.

[Justification of Inclusion Criteria]

- 1, 2 : These criteria were set to include subjects who understand the objective of the study and will cooperate in the study conduct.
- 3 : This criterion was set as this study is designed to conduct with subjects who have completed the 26-week treatment period in the preceding study.
- 4 : This criterion was set in consideration of subject safety.
- 5 : This criterion was set in consideration of safety risk associated with pregnancy.

7.2 Exclusion Criteria

Any subject who meets the following criteria will not qualify for entry into the study:

1. The subject is an immediate family member, study site employee, or is in a dependant relationship with a study site employee who is involved in conduct of this study (e.g., spouse, parent, child, sibling) or may consent under duress.
2. Subject has donated 400 mL or more of his or her blood volume within 90 days prior to the initiation of the investigational drug in this study.
3. The subject is required to receive excluded medications or treatments.
4. If female, the subject is intending to become pregnant during, or within 1 month after the last dose of the investigational drug; or intending to donate ova during such time period.
5. The subject requires surgery or hospitalization for surgery during the study period.
6. The subject who, in the opinion of the investigator or sub-investigator, is unsuitable for any other reason.

[Justification of Exclusion Criteria]

- 1, 5 : These criteria were set as basic matters to conduct clinical studies.
- 2 : This criterion was set as basic matters to conduct clinical studies in consideration of subject safety.
- 3 : This criterion was set in consideration of efficacy evaluation and subject safety.
- 4 : This criterion was set to avoid the safety risk associated with pregnancy to pregnant woman and fetus.
- 6 : This criterion was set to exclude subjects with unknown factors which might influence the evaluation of efficacy.

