13.3 Determination of Sample Size

Number of subjects to be enrolled in this study: approximately 182

[Justification of Sample size]

In the preceding study, the planned number of subjects to be randomized was a total of 240 (120 per group) and the planned number of subjects evaluable for the primary endpoint (change in the MDS-UPDRS Part II + Part III total score from baseline to Week 26 of the treatment period (LOCF)) was a total of 220 (110 per group).

Since this study is a long-term extension study in patients with early Parkinson's disease who have completed the 26-week treatment period in the preceding study, considering the potential dropouts in the preceding study, approximately 182 subjects will be enrolled in this study.

In addition, considering the potential dropouts in this study and in the preceding study, it is estimated that 155 subjects will be treated with 1 mg of TVP-1012 for 26 weeks and 59 subjects for 52 weeks.

CONFIDENTIAL

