7.3 Excluded Medications and Treatments

The list of excluded medications and treatments is shown in Table 7.a. Subjects must be instructed not to take any medications, including over-the-counter products, without first consulting with the investigator or sub-investigator.

Table 7.a Excluded Medications and Treatments

Medication/Treatment	Duration	Exception
Excluded Medication		
(1) selegiline	From VISIT 8 through VISIT 14, or the day of study site visit for early termination.	—
(2) pethidine, tramadol	From VISIT 8 through VISIT 14, or the day of study site visit for early termination.	—
(3) reserpine, methyldopa	From VISIT 8 through VISIT 14, or the day of study site visit for early termination.	—
(4) Other investigational drug	From VISIT 8 through VISIT 14, or the day of study site visit for early termination.	—
(5) levodopa containing drug		
(6) Dopamine agonist		
(7) amantadine	From VISIT 8 through VISIT 14, or the day of study site visit for early termination.	—
(8) Anticholinergic agent		
(9) COMT inhibitor		
(10) droxidopa		
(11) zonisamide	From VISIT 8 through VISIT 14, or the day of study site visit for early termination.	—
(12) istradefylline		
(13) Psychoneurotic agent (phenothiazine, butyrophenone, benzamide, Atypical antipsychotic drug)	From VISIT 8 through VISIT 14, or the day of study site visit for early termination.	Quetiapine may be concomitantly administered without change in dose regimen throughout the study if the drug has been continuously administered in the preceding study.
(14) Antinauseant with dopamine agonistic property	From VISIT 8 through VISIT 14, or the day of study site visit for early termination.	domperidone may be concomitantly administered without change in dose regimen throughout the study if the drug has been continuously administered in the preceding study.
(15) CYP1A2 inhibitor (including ciprofloxacin, enoxacin, fluvoxamine, zafirlukast)	From VISIT 8 through VISIT 14, or the day of study site visit for early termination.	—

CONFIDENTIAL

Medication/Treatment	Duration	Exception
(16) dextromethorphan	From VISIT 8 through VISIT 14, or the day of study site visit for early termination.	—
(17) Antidepressant	From VISIT 8 through VISIT 14, or the day of study site visit for early termination.	—
(18) St. John's Wort (including supplements)	From VISIT 8 through VISIT 14, or the day of study site visit for early termination.	—

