##### 2.1.1.2 Analysis based on the data after study drug administration for the treatment period in the preceding study

Analysis Set: Full Analysis Set 2

Analysis Variable(s): MDS-UPDRS Part II + Part III total score

Visit: Baseline (at end of observation period), Week 6, Week 10, Week 14, Week 20, Week 26, Week 32, Week 36, Week 40, Week 46, Week 52 of Treatment Period, Week 52 of Treatment Period (LOCF)

Analysis Method(s): The same analysis as 2.1.1.1 will be performed for the above analysis variables. Furthermore, the point estimates of the mean differences between treatment groups (1 mg → 1 mg group-P → 1 mg group) and the two-sided 95% confidence intervals at each visit by treatment group in the preceding study will be provided for the change from baseline (at end of observation period) in the MDS-UPDRS Part II + Part III total score at each visit during the treatment period (at each visit during the treatment period (Week 6 to Week 52 of Treatment Period (LOCF))-Baseline (at end of observation period)).

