### **2.3.2 Handling of Dropouts or Missing Data**

Missing test results and data determined to be non-evaluable according to the Handling Rules for Analysis Data and this statistical analysis plan will not be used for hypothesis testing and estimations. Values below/less than or equal to the lower limit of quantification will be treated as zero when calculating the descriptive statistics. Values above/greater than or equal to the upper limit of quantification will be treated as the upper limit of quantification when calculating the descriptive statistics.

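### The between-group differences at Weeks 32–52 in SAP 2.1.1.2 rest on subjects selected after randomisation and are at risk of selection bias of unknown direction and size

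*Protocol*

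**What the plan says.** The arms compared were randomised in the preceding study, CCT-001. Entry to the extension is decided at VISIT 8 (Week 26). Protocol 7.1 requires completion of CCT-001 (criterion 3) and, in criterion 4, "The subject has shown no safety issues during the study treatment in the preceding study, in the judgment of the investigator or sub-investigator". Protocol 7.2 criterion 3 bars a subject if "The subject is required to receive excluded medications or treatments"; Table 7.a in Section 7.3 lists levodopa, dopamine agonists and other antiparkinsonian drugs among these.

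Protocol 13.3 starts from 240 randomised (120 per group), then states that "approximately 182 subjects will be enrolled in this study" and that "it is estimated that 155 subjects will be treated with 1 mg of TVP-1012 for 26 weeks and 59 subjects for 52 weeks". It gives no dropout rate, overall or by arm.

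SAP 2.1.1.2 adds "the point estimates of the mean differences between treatment groups" (1 mg->1 mg minus P->1 mg), with two-sided 95% confidence intervals, for change from the CCT-001 baseline at each visit from Week 6 to Week 52, plus a Week 52 (LOCF) row. The set is Full Analysis Set 2 (FAS 2), whose definition is left to the Handling Rules for Analysis Data. Under SAP 2.3.2, missing and non-evaluable data "will not be used for hypothesis testing and estimations". SAP 2.3.1 applies no covariate adjustment, and no sensitivity analysis for selection is described.

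**The concern.** At Weeks 6–26 a randomised subject can contribute whether or not he or she later enters the extension. At Weeks 32–52 only entrants have scores. The rows look like one series but may describe different populations, and nothing in the SAP says so.

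The conditions that separate the two populations are outcomes of the first 26 weeks. Completion, safety and need for another antiparkinsonian drug can each depend on whether the subject took placebo or 1 mg, and the last is closely tied to the score being analysed. If the subjects removed differ between arms in their scores, the raw difference among those who remain is shifted.

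This is the only between-group efficacy estimate planned; Protocol 13.1.3 has none. Printed with 95% intervals to Week 52, it invites a reading as early versus delayed start, which needs comparable groups.

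**Working it through.** **1. The plan's own figures.** 182/240 = 75.8%, so 58 randomised subjects (24.2%) are expected to have no extension data. No rates are stated, so the counts cannot be derived from stated inputs. Equal rates in both arms of 20% dropout in CCT-001, 95% roll-over and 35% dropout in the extension fit them:

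- 120 × 0.80 = 96 completers per arm
- 96 × 0.95 = 91.2 entrants per arm (182.4 in total)
- 91.2 × 0.65 = 59.3 per arm at Week 52
- 96 + 59 = 155 treated for 26 weeks

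Three rates were fitted to three counts. This shows that the counts are compatible with equal rates; it does not confirm them.

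**2. Assumptions, none from the documents.** SD of change 8–10 points; Week 26–52 correlation r = 0.5–0.7; correlation ρ of the latent non-entry decision with Week 26 change = 0.3–0.7; 59 subjects per arm at Week 52. The 59 in the placebo arm is itself assumed. Higher scores are worse (SAP Appendix 3).

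**3. Formula.** If a share p of an arm is kept and the worst tend to leave, the mean Week 52 change of those kept falls by SD × r × ρ × L(p), where L(p) = φ(z_p)/p. So

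bias of (1 mg minus placebo) = SD × r × [ρ_P L(p_P) − ρ_1 L(p_1)].

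The 95% half-width is 1.96 × SD × √(2/59), which is 2.89 at SD 8 and 3.61 at SD 10. Coverage is Φ(1.96 − b/SE) − Φ(−1.96 − b/SE).

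**4. Results.**

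- *Identical selection, equal entry:* bias 0.
- *One worsening-driven rule in both arms, groups 3–5 points apart at Week 26, 182 entering in total:* entry runs from about 93 v 89 to 99 v 83 (1 mg v placebo). Upper end: L is about 0.31 on 1 mg and 0.51 on placebo, so 8 × 0.7 × 0.7 × 0.20 = 0.78. Range about +0.1 to +0.8 points; coverage about 92–95%.
- *Placebo only, all losses from 120 to 91 driven by Week 26 score:* L(91/120) = 0.4115. From 8 × 0.5 × 0.3 × 0.4115 = 0.49 to 10 × 0.7 × 0.7 × 0.4115 = 2.02 points; coverage 94% down to about 81%.
- *Placebo only, acting just at VISIT 8 (91 of 96, equal rates per arm):* L(91/96) = 0.1124. From 8 × 0.5 × 0.3 × 0.1124 = 0.13 to 10 × 0.7 × 0.7 × 0.1124 = 0.55 points; coverage 94–95%.
- *1 mg only:* the last two ranges with the opposite sign.

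The two placebo-only cases have equal entry in both arms, so equal entry rates would not rule bias out. Dropout during the extension is a further selection that these figures leave out.

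**5. The LOCF row.** Its window is days 1 to 385 and it takes the last evaluable value. If FAS 2 includes non-entrants, their value from Week 26 or earlier is reported as Week 52, and in the placebo arm that value was obtained before any TVP-1012. If FAS 2 excludes them, the row is selected like the others. Neither repairs the comparison.

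**6. What a repeated-measures model gains.** Ratio of its SE to the raw SE = √(59 × [(1 − r²)/59 + r²/n]), where n per arm have Week 26 scores. For n = 120: 0.934 (r = 0.5) and 0.867 (r = 0.7). For n = 96: 0.951 and 0.901. The SE falls by about 5–13%.

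**The case against.** The criteria are worded identically for both previous arms, no rates by arm are given, and the planning counts fit equal rates. A reader might infer that the criteria do act differently on placebo and 1 mg, that the differences are biased, and that the bias runs against early start. The documents support none of these as fact. Worsening on placebo would push the difference upward, but safety exclusions on 1 mg could move it either way. This part of the objection stands.

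A reader might also take 2.0 points and 81% coverage as the expected effect. That needs score-driven loss on placebo only, with all 24% of losses governed by Week 26 score. Protocol 13.3 attributes the fall from 240 to 182 to dropout in CCT-001; on the equal-rate reading, VISIT 8 removes only about 5 per arm. This stands too.

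The consequence is limited: adverse events are the primary endpoint, no significance level is set, no delayed-start objective appears, and SAP 1.1.6.2 already tabulates discontinuation reasons by previous arm for all randomised subjects. That caps the weight of the point without answering it. The table corrects no estimate, and SAP 1.1.3 covers only those who consented and is not specified by arm. Identical wording does not secure comparability either: one worsening-driven rule removes more subjects from whichever arm worsens more.

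**Conclusion.** The point holds as a risk. The observed-case differences at Weeks 32–52 are conditional on events after randomisation, and the SAP neither says so nor offers an analysis that uses the non-entrants' earlier scores. Under the stated assumptions the shift ranges from nil, through about 0.1–0.8 points under a common worsening-driven rule, to 2.0 points in the extreme one-arm case, with either sign possible. Most of this range is small beside a half-width of 2.9–3.6 points. Whether FAS 2 already contains non-entrants cannot be told from these documents. Because the analysis is secondary and descriptive, this is a recommended improvement and no threat to the study's primary objective.

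**What to change.** In SAP 2.1.1.2:

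1. Keep the raw means and differences as description, and label Weeks 32–52 as conditional on extension entry and not protected by randomisation.
2. Add a mixed model for repeated measures (group, visit, group × visit, unstructured covariance) on all Week 6–52 change scores of all randomised subjects with post-baseline data, whether or not they entered OCT-001, and report its visit-wise differences. Confirm or set FAS 2 accordingly.
3. Report the Week 26 difference twice, for all of FAS 2 and for entrants only, with the mean of each previous arm, so that any shift at entry is visible.

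The cost is SAP wording, one model and one extra row; no new data are needed. The model assumes missing at random. That is plausible because Week 26 scores are recorded at VISIT 8, but it is not guaranteed: consent precedes those assessments (Protocol 9.1.1), and entry also turns on investigator judgement that no score captures. The model removes bias fully only if selection depends on recorded scores, so it should stand beside the descriptive rows and not be presented as a cure.
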